[figure not shown]
[figure not shown]

[figure not shown]
[figure not shown]

## CLINICAL TRIAL PROTOCOL SYNOPSIS

Name of company:		Boehringer Ingelheim	
Name of finished product:		NA	
Name of active ingredient:		Nintedanib	
Protocol date: 30 May 2017	Trial number: 1199.225		Revision date: 13 Aug 2020
Title of trial:	An open-label extension trial to assess the long term safety of nintedanib in patients with 'Systemic Sclerosis associated Interstitial Lung Disease' (SSc-ILD) SENSISCIS ® - ON		
Coordinating Investigator:			
Trial site(s):	Multi-centre trial conducted in approximately 30 countries; identical to sites which enrolled patients into 1199.214 and into 1199-0340		
Clinical phase:	III		
Objective(s):	The primary objective of this trial is to assess the long-term safety of nintedanib treatment in patients with Systemic Sclerosis associated Interstitial Lung Disease who have completed (did not prematurely discontinue trial medication) the phase III parent trial SENSISCIS ® (1199.214) and to assess the safety of the ongoing nintedanib treatment in patients with Systemic Sclerosis associated Interstitial Lung Disease who have completed the phase I drug-drug interaction (DDI) trial 1199-0340.		
Methodology:	Extension trial to evaluate the long term tolerability and safety of Nintedanib		

Name of company:		Boehringer Ingelheim	
Name of finished product:		NA	
Name of active ingredient:		Nintedanib	
Protocol date: 30 May 2017	Trial number: 1199.225		Revision date: 13 Aug 2020
No. of patients:			
total entered:	Approximately 400 patients		
each treatment:	Not applicable		
Diagnosis:	Systemic Sclerosis associated Interstitial Lung Disease		
Main criteria for inclusion:	Patients who have completed (did not prematurely discontinue trial medication) SENSICIS ® (1199.214) or 1199-0340.		
Test product(s):	Nintedanib		
dose:	Nintedanib 150 mg bid (300 mg daily) or 100 mg bid (200 mg daily)		
mode of administration:	p. o.		
Comparator products:	Not applicable		
dose:			
mode of administration:			
Duration of treatment:	Treatment duration for each patient will be variable. Treatment will be stopped if a reason for withdrawal is met. The trial is estimated to last approximately 34 months.		

Name of company:		Boehringer Ingelheim	
Name of finished product:		NA	
Name of active ingredient:		Nintedanib	
Protocol date: 30 May 2017	Trial number: 1199.225		Revision date: 13 Aug 2020
Endpoints	The primary endpoint is the incidence of overall adverse events over the course of the extension trial.		
Safety criteria:	Adverse events, physical examination including weight, vital signs, laboratory evaluations.		
Statistical methods:	Descriptive statistics of adverse events and other safety parameters.		

FLOWCHART

Visit*	1 	2 	2a	3	3a	4	4a	5	5a	6	6a	7	Xa 	X 	EOT 	FU 
	Screening	Open Label Treatment Period														FU
Week		0	2	4	8	12	18	24	30	36	44	52	60 + every 16w	68 + every 16w		
Day Time window (days)		1	15 ±3	29 ±3	57 ±3	85 ±3	127 ±7	169 ±7	211 ±7	253 ±7	309 ±7	365 ±7	±7	±7		+7
Informed consent	X 															
Demographics	X															
In-/Exclusion criteria		X														
Baseline Conditions	X	X														
Physical examination, vital signs	X	X		X		X		X		X		X		X	X	X
Adverse events, conc. therapy	X 	X 		X		X		X		X		X		X	X	X
12-lead ECG		X						X				X				
Safety Laboratory (blood and urine)	X	X	X 	X	X 	X	X 	X	X 	X	X 	X	X 	X	X	
Pregnancy test 		X	X	X	X	X	X	X	X	X	X	X	X	X	X	X
Optional biobanking sample 		X										X				
																
																
																
IRT call/notification		X		X		X		X		X		X		X	X	
Dispense trial medication		X		X		X		X		X		X		X		
Collect trial medication				X		X		X		X		X		X	X	
Compliance / drug accountability				X		X		X		X		X		X	X	
Termination of trial medication															X	
Conclusion of patient participation																X

**Footnotes:**

\*In case of dose change (reduction or re-escalation) additional visits have to be included (refer to [Section 6.2.4](#))

 Visit 1 should occur at least one day after trial completion of SENCIS® (Follow up Visit) or 1199-0340 (End of Treatment/end of Study Visit). Visit 2 of this extension trial is to be scheduled:

- within a maximum of 12 weeks after last drug intake in SENCIS® (please see also [Section 6.2.1](#))
- within a maximum of 1 week after last drug intake in 1199.340

 Combining of Visit 1 and Visit 2:

- For patients who completed SENCIS®, Visit 1 and Visit 2 may occur on the same day if the period between the last available laboratory test within SENCIS® and Visit 2 of the extension trial (1199.225) is ≤ 6 weeks.
- For patients who completed 1199-0340, Visit 1 and Visit 2 are always scheduled on the same day.

If medical condition is not stable and new Adverse Events occurred, a new laboratory test has to be performed. For patients performing Visit 1 and Visit 2 on the same day, eligibility assessment will be based on laboratory data from last laboratory test available within SENCIS® / 1199-0340. In case Visit 1 and Visit 2 takes place on the same day, laboratory tests, physical examination and vital signs are performed only once on that day and are recorded under Visit 2 in the eCRF

 The patient is required to sign informed consent prior to any trial related activities

 Only medical conditions that are occurring concomitantly at the time of screening will be recorded as baseline conditions in the eCRF, including any ongoing AEs from SENCIS® or 1199-0340 respectively.

 Cautionary note: dependent on concomitant treatment additional safety monitoring should be considered at discretion of the investigator. Intermediate lab tests (a-Visits) do not necessarily need to be a site visit.

 β-HCG will be performed at central lab at Visit 2 only. Urine dipstick pregnancy tests will be provided centrally and should be performed in all women of childbearing potential every 4-6 weeks: at least every visit and if necessary, additionally at home or at a local doctor / laboratory. If urine test is not acceptable to local authorities, a blood test can be done at a local laboratory. Woman of childbearing potential will be instructed accordingly

 Only after the dedicated biobanking Informed Consent has been received

 Self-reported outcome questionnaires must always be done by patients in a quiet place prior to any other visit procedure

 Same scheme should be repeated as often as needed: one complete visit every 16 weeks and one intermediate visit (a-visit) in between (every 16 weeks)

 End of Treatment Visit to be performed if a reason for withdrawal is met (refer to [Section 3.3.4](#))

[figure not shown]
 A follow-up (FU) visit should be planned for 7 days after last drug intake in case trial medication had to be discontinued permanently due to adverse events

 At selected sites (if the locally required language version is available)

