### 5.2.11.2 Adverse event collection and reporting

#### **AE Collection**

The investigator shall maintain and keep detailed records of all AEs in their patient files.

The following must be collected and documented on the appropriate CRF(s) by the investigator:

- From signing the informed consent onwards through the Residual Effect Period (REP), of at least 28 days until individual patient's end of trial:  
-all AEs (serious and non-serious) and all AESIs.
- After the individual patient's end of trial:  
the investigator does not need to actively monitor the patient for AEs but should only report relevant SAEs and relevant AESIs of which the investigator may become aware of by any means of communication, e.g. phone call. Those AEs should however, not be reported in the CRF.

[figure not shown]

Figure 5.2.11.2: 1 AE collection

The REP is defined as 28 days after the last trial medication application and will apply only to patients that discontinue the trial early. All AEs which occurred through the treatment phase and throughout the REP will be considered as on treatment, please see [Section 7.3.4](#). Events which occurred after the REP will be considered as post treatment events.

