### **End of Treatment (EOT)**

If a reason for drug discontinuation is met or the trials terminated due to one of the reasons mentioned in [Section 3.3.4](#) an End of treatment Visit (EOT) should be scheduled as soon as possible after last drug intake. Reason for discontinuation must be documented in the eCRF.

For detailed description of the trial procedures at the EOT visit, please refer to the [Flowchart](#).

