### 6.2.3 Trial Completion and Follow Up Period

The End of Treatment Visit will be the trial completion visit. A Follow-up (FU) Visit is only to be planned for 7 days after last trial drug intake in case trial medication had to be discontinued permanently due to adverse events.

For detailed description of the trial procedures at the FU Visit, please refer to the [Flowchart](#).

If the reason for removal of a patient from the treatment is an adverse event or an abnormal laboratory test result, the patient must be followed until complete resolution or stabilization of the event for at least 7 days after onset of the event or until follow-up is considered adequate by the investigator and the clinical monitor.

A patient will be considered lost to follow-up if the investigator is not able to contact him/her despite multiple attempts. Every effort must be made; at least 2 telephone contacts plus 1 mailing should be documented. The site must notify the clinical monitor prior to designating a patient as lost to follow-up.

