7.8.1 Adverse events

Unless otherwise specified, the analyses of adverse events will be descriptive in nature. All analyses of AEs will be based on the number of subjects with AEs and NOT on the number of AEs.

For analysis multiple AE occurrence data on the CRF will be collapsed into an AE provided that all of the following applies:

- All AE attributes are identical (LLT, intensity, action taken, therapy required, seriousness, reason for seriousness, relationship [investigator defined drug-relatedness], outcome, AE of special interest).
- The occurrences were time-overlapping or time-adjacent (time-adjacency of 2 occurrences is given if the second occurrence started on the same day or on the day after the end of the first occurrence).

For further details on summarisation of AE data, please refer to [\(2,3\)](#).

The analysis of adverse events will be based on the concept of treatment emergent adverse events. That means that all adverse events occurring between first drug intake in extension trial till last drug intake + 7 days will be assigned to the on-treatment period and described according to randomised treatment in parent trial. All adverse events occurring before first drug intake will be assigned to 'previous trial', 'Between-trials' or 'screening'.

All adverse events occurring after the last trial drug intake will be assigned to 'residual effect period' or 'follow-up' or 'post-study' (for listings only). For details on the treatment definition, see [Section 6.1](#).

According to ICH E3 (4), AEs classified as 'other significant' needs to be reported and will include those non-serious and non-significant adverse events with

- (i) 'action taken = drug withdrawn' or 'action taken = dose reduced', or
- (ii) marked haematological and other lab abnormalities or lead to significant concomitant therapy

An overall summary of adverse events will be presented by randomised treatment in parent trial (and Total).

The frequency of patients with AEs will be summarised by randomised treatment in parent trial (and Total), primary system organ class (SOC) and preferred term (PT). This will be presented using a >5% cut-off in the CTR and repeated without the cut-off in the CTR appendices.

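### The seven days after the last dose count as on-treatment for every patient, but a contact covering them is scheduled only when an adverse event caused the stop

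*Protocol*

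**What the plan says.** **Schedule.** On the follow-up contact (FU), Flowchart footnote 11 reads: "visit should be planned for 7 days after last drug intake in case trial medication had to be discontinued permanently due to adverse events". Protocol 6.2.3 repeats the restriction: the FU "Visit is only to be planned for 7 days after last trial drug intake in case trial medication had to be discontinued permanently" because of adverse events. For everyone else, "The End of Treatment Visit will be the trial completion visit". The End of Treatment (EOT) visit "should be scheduled as soon as possible after last drug intake", with no minimum or maximum interval.

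**Collection.** Protocol 5.2.11.2 requires all AEs to be collected "From signing the informed consent onwards through the Residual Effect Period (REP), of at least 28 days", until the individual end of trial. It adds that this period "will apply only to patients that discontinue the trial early". After the end of trial, active monitoring stops. Only relevant SAEs and AEs of special interest that reach the investigator are reported, and "Those AEs should however, not be reported in the CRF".

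**Analysis.** Protocol 7.3.4 sets the residual effect period (REP) at 7 days for all treated patients. SAP 7.8.1 follows it: "all adverse events occurring between first drug intake in extension trial till last drug intake + 7 days will be assigned to the on-treatment period". SAP 6.1 marks several periods as optional, but not the REP, and counts the REP as on-treatment. In SAP 7.8.1.5 the time at risk of an event-free patient ends at last intake + 7 days or at database lock, whichever is earlier. Last contact plays no part.

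**End of participation.** The Flowchart marks the conclusion of participation only in the FU column. Section 6.2.3 places trial completion at EOT.

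**The concern.** One on-treatment definition covers all patients, but the schedule supports its last seven days in only one kind of stopper. A patient who stops because of an AE is seen again at about day 7. A patient who stops for non-compliance, site closure or access to nintedanib elsewhere may have a last contact on or near the day of the last dose. An event on day 4 is likely to be found in the first patient and may be missed in the second. The second patient's silent days still enter the denominator as event-free.

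Stops without an AE are built into the design. Section 3.1 lets patients leave once they have outside access to nintedanib, Section 3.3.4.4 lets the sponsor close the trial or a site on marketing authorisation, and Section 1.2 reports approvals in this indication in 2019 and 2020. At stake are the completeness of the tables, above all those for serious and fatal events, where single cases count, and slightly low incidence rates.

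**Working it through.** The plan gives no sample size calculation, event count or rate to reproduce. The check compares the windows first and then sizes the gap.

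**1. Windows side by side**

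| | Stop due to AE | Any other stop |
|---|---|---|
| Last scheduled contact | FU, day 7 (Flowchart window +7) | EOT, as soon as possible |
| On-treatment window (7.3.4, SAP) | last intake + 7 days | last intake + 7 days |
| Time at risk if event-free (SAP 7.8.1.5) | last intake + 7 days | last intake + 7 days |
| Scheduled contact reaches day 7? | yes | not required |

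Against the 28-day period in 5.2.11.2, the FU covers 7/28 = 25% to 14/28 = 50%, so under that rule AE stoppers are not fully covered either.

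**2. SAEs in the unobserved window**

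Inputs: 400 + 14 = 414 patients (Protocol 3.1). Assumed, because the documents do not say: 30-80% stop for reasons other than an AE, the SAE rate is 10-40 per 100 patient-years, and none of the seven days is observed.

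- Patients: 414 × 0.30 = 124; 414 × 0.80 = 331.
- Patient-years: 124 × 7/365.25 = 2.4; 331 × 7/365.25 = 6.3.
- SAEs: 2.4 × 0.10 = 0.2; 6.3 × 0.40 = 2.5.

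The SAP counts patients with events, so fewer patients than this would be added to the tables.

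**3. Incidence rate of a rare event**

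With share s of non-AE stops, mean exposure T days and a constant hazard, the relative understatement is s × 7/(T + 7). T is assumed.

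| T (days) | 7/(T + 7) | s = 0.30 | s = 0.80 |
|---|---|---|---|
| 182 | 3.70% | 1.1% | 3.0% |
| 365 | 1.88% | 0.6% | 1.5% |
| 730 | 0.95% | 0.3% | 0.8% |
| 1095 | 0.64% | 0.2% | 0.5% |

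**4. Primary endpoint (% of patients with any AE)**

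If proportion p has had an AE by day T, with λ = −ln(1 − p)/T, the share whose first AE falls in the seven days is (1 − p)(1 − e^(−7λ)).

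- p = 80%, T = 182: 1.20 percentage points.
- p = 98%, T = 730: 0.07 percentage points.

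These values assume that every patient is unobserved. Applying the shares gives 0.30 × 0.07 = 0.02 to 0.80 × 1.20 = 0.96 percentage points.

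A hazard that rises after stopping would make the figures in steps 3 and 4 larger. The documents give no basis for sizing that.

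**The case against.** The strongest reply is that Section 5.2.11.2 already obliges the investigator to record all AEs through the REP, whatever the reason for stopping, and does not tie this to a visit. EOT also records AEs and has no fixed day, so it may fall some days into the window. The requirement to follow AEs to resolution continues beyond the end of trial.

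This defeats one tempting inference: that residual-period events are simply not collected after non-AE stops. The documents show only that no contact is scheduled to collect them. The rest of the reply is weaker. Nothing makes EOT reach day 7, following known events does not detect new ones, and if EOT is the end of trial, the same section ends active monitoring and keeps later events out of the CRF. Whether EOT is the end of trial is itself unclear, because the Flowchart points to FU. The AE-collection figure, which might settle this, is not reproduced in the text available for this review.

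A reader might also infer that the REP length is irrelevant. It is not. The 28-day rule covers only early discontinuers, a group the protocol does not define for outside access or site closure, and a contact at the end of the REP cannot be timed until the length is settled.

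Nor should a 28-day count of missed SAEs be charged to the on-treatment tables. Under 7.3.4 and the SAP, events after day 7 fall outside them even when recorded.

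Finally, the analysis is descriptive and tabulated by parent-trial group and in total, with no comparison by reason for stopping. That limits the consequences but does not remove the gap.

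**Conclusion.** The inconsistency is real and is in current text: the plan analyses a seven-day window for everyone but schedules a contact covering it only after AE-related stops. Ascertainment therefore differs by reason for stopping, and unobserved days are counted as event-free time.

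The size is small: about 0.2-2.5 SAEs in the window, rare-event rates low by about 0.2-3.0% in relative terms, and about 1 percentage point or less on any-AE incidence. All three rest on assumed shares of non-AE stops, event rates and exposure, and on none of the window being observed. They are upper limits to the extent that EOT falls late or sites ask about later events anyway. The documents do not support calling this a material bias in the primary endpoint. It deserves correction because the SAE and fatal-AE tables can turn on one or two cases and because the remedy is cheap.

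**What to change.** 1. **Reconcile the REP length** between Protocol 5.2.11.2 (28 days, early discontinuers) and Protocol 7.3.4 and the SAP (7 days, all treated patients), and state which patients it covers.
2. **Schedule the contact.** In Flowchart footnote 11 and Section 6.2.3, plan an AE contact at or after the end of the reconciled REP for every patient who stops nintedanib. A telephone call is enough when no AE caused the stop; Appendix 10.3 already accepts remote AE collection in exceptional circumstances. After withdrawal of consent, the contact needs the patient's agreement, as Section 3.3.4.3 requires for follow-up. Enter its AEs in the eCRF and mark the conclusion of participation at this contact, so that the Flowchart, 6.2.3 and 5.2.11.2 agree on the end of trial.
3. **Amend the SAP.** In 7.8.1.5, end time at risk at the earliest of last intake + REP, last contact and database lock; SAP 6.1 already uses a last-contact date from the CRF. For patients who have left without the contact, show residual-period events by reason for stopping (AE or other). The cap aligns the rates with observed time, but it recovers no events and does not change the patient percentages, so it does not replace item 2.

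Cost: protocol, eCRF and SAP wording, one call per patient, and an individual end of trial that falls somewhat later.

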## ABBREVIATIONS

AE	Adverse Event
ACE	Angiotensin-Converting-Enzyme
ACR	American College of Rheumatology
AE(s)	Adverse Event(s)
AESI	Adverse Event of Special Interest
ALK	Alkaline Phosphatase
ALT	Alanine Aminotransferase
(anti-)RNA Pol	Anti-RNA polymerase III Antibodies
AST	Aspartate Aminotransferase
ATS / ERS	American Thoracic Society / European Respiratory Society
AUC	Area Under the Curve
BI	Boehringer Ingelheim
bid	Bis in die (twice daily dosing)
BNP	Brain Natriuretic Peptide
CA	Competent Authority
CI	Confidence Interval
CK	Creatine Kinase
Cmax	Maximum measured concentration of the analyte in plasma
CML	Local Clinical Monitor
CNS	Central Nervous System
CO	Carbon Monoxide
COPD	Chronic Obstructive Pulmonary Disease
CRA(s)	Clinical Research Associate(s)
CRO	Clinical Research Organisation
CT	Concomitant Therapy
CTCAE	Common Terminology Criteria for Adverse Events
CTP	Clinical Trial Protocol
CTR	Clinical Trial Report
CYP3A4	Cytochrome P450 3A4
DDI	Drug-Drug Interaction
DEDP	Drug Exposure during Pregnancy
DILI	Drug-Induced Liver Injury
dL	Decilitre
DoH	Declaration of Helsinki
█	█
EC	Ethics Committee
ECG	Electrocardiogram
eCRF	Electronic Case Report Form
e.g.	Example given
EMA	European Medicines Agency
EOT	End of Treatment
EudraCT	European Clinical Trials Database
EULAR	European League against Rheumatism
FDA	Food and Drug Administration

FEV 1	Forced Expiratory Volume in 1 second
FGFR	Fibroblast Growth Factor Receptor
FU	Follow-up
█	█
g	Gram
GAVE	Gastric antral vascular ectasia
GCP	Good Clinical Practice
GGT	Gamma-Glutamyl Transferase
GI	Gastrointestinal
GIT	Gastrointestinal tract
GLI	Global Lung Initiative
GP	General Practitioner
h	Hour
█	█
Hb	Haemoglobin
HCG	Human chorionic gonadotropin
Hct	Haematocrit
IB	Investigator's Brochure
ICH	International Conference on Harmonisation
i.e.	id est
IEC	Independent Ethics Committee
ILD	Interstitial Lung Disease
INR	International Normalised Ratio
IPF	Idiopathic Pulmonary Fibrosis
IRB	Institutional Review Board
IRT	Interactive Response Technology
ISF	Investigator Site File
I.U. s. c.	International Unit sub cutaneous
Lck	Lymphocyte-specific protein tyrosine kinase
LDH	Lactate Dehydrogenase
Lyn	Lymphocyte antigen receptor-associated tyrosine kinases
MedDRA	Medical Dictionary for Drug Regulatory Activities
mg	Milligram
min	Minute
mL	Millilitre
mm	Millimetre
mmHg	Millimetres of mercury
mmol	Millimolar
█	█
nRTK	Non-Receptor Tyrosine Kinase
PAH	Pulmonary Arterial Hypertension
(p) PDGF / R	(polyclonal) Platelet Derived Growth Factor / Receptor
PFT	Pulmonary Function Test
P-gp	P-glycoproteine (MDR1)
PH	Pulmonary Hypertension
PI / IC	Patient Information / Informed Consent
p. o.	per os (oral)

PT	Prothrombin Time
PTT	Partial Thromboplastin Time
QT	Interval in the electrocardiogram from the onset of the QRS complex to the end of the T wave
RBC	Red Blood Cells
RDC	Remote Data Capture
REP	Residual Effect Period
(m)RNA	(messenger) Ribonucleid Acid
RTK	Receptor Tyrosine Kinase
SAE	Serious Adverse Event
SENSCIS®	Safety and Efficacy of Nintedanib in Systemic Sclerosis
[REDACTED]	[REDACTED]
SOP	Standard Operating Procedure
SpO 2	Saturation of oxygen
Src	Rous sarcoma viral oncogene
SSc	Systemic Sclerosis
SUSAR	Suspected Unexpected Serious Adverse Reactions
TCM	Trial Clinical Monitor
TMF	Trial Master File
TSAP	Trial Statistical Analysis Plan
UGT1A1	UDP-glucuronosyltransferase polypeptide A1
ULN	Upper Limit of Normal
[REDACTED]	[REDACTED]
VEGF / R	Vascular Endothelial Growth Factor / Receptor
wk	Week
WOBC	Women of childbearing potential
WONCBP	Women of non-childbearing potential

